Précis	A total of 700 subjects will be enrolled. To measure the incidence of contrast-induced nephropathy (CIN), subjects (n = 600) with suspected pulmonary embolism (PE) will be prospectively randomized to CT of the pulmonary arteries (CTPA, iodinated contrast media exposure) or to ventilation-perfusion scintigraphy (VQ, unexposed control). To validate a risk-stratification tool for AKI, alone and in combination with acute-phase markers of renal dysfunction (Cystatin-C and NGAL) in both the exposure and unexposed controls, as well as, an additional non-randomized 100 subjects who will undergo CTPA for suspected PE. All subjects will be followed for the development of acute kidney injury (AKI) occurring ≥ 48 hours and ≤ 168 hours following imaging and subsequent long-term outcomes.
Primary Study Objective	Compare the incidence of acute kidney injury (AKI) consistent with contrast-induced nephropathy (CIN) in 600 patients with suspected PE and an AKIrisk Score ≥ 2 , randomized to CTPA (contrast media exposure) or VQ (unexposed control) imaging.
Secondary Study Objectives	
 1) Validate the AKIRisk score, alone and in combination with acute-phase markers of renal dysfunction (Cystatin-C and/or NGAL), to inform imaging strategies and reduce the risk of CIN. 2) Compare the incidence of AKI and subsequent severe health outcomes in patients exposed to iodinated contrast media and unexposed controls at 30-days and 1-year. 3) Measure the 30-day and 1-year incidence of VTE and subsequent severe health outcomes including outcomes related to VTE and VTE treatment
Safety Objectives	Compare the safety outcomes in both the CTPA and VQ groups including outcomes associated with imaging type, VTE (diagnosed and missed), and treatment of VTE occurring within 7 days of enrollment study imaging.
Primary Endpoint	AKI consistent with CIN, defined as an increase in creatinine $\geq 25\%$ of baseline or an absolute increase in creatinine to ≥ 0.5 mg/dL ≥ 48 hours and ≤ 168 hours of the enrollment PE imaging study.

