The 45-day incidence of VTE in patients with a calculated pre-test risk between 2.5% and 20% was 3%. Importantly, the accepted test threshold prompting imaging for suspected PE is very low: only 2.5%.^{13,48} As such, <15% of patients who underwent imaging for suspected PE ultimately were ultimately diagnosed with VTE. Pre and post-CTPA creatinine data were available for 30% of a validation subset (834 patients from 4 institutions)

[figure not shown]

Figure 3. Example output of the PE PreTest Consult Score (<http://pretestconsult.com/v21/pe>), which allows clinicians to calculate the point-estimate of an individual patient's pre-test probability of pulmonary embolism, at the bedside, using an attribute matching method leveraging over 2 decades of data, from over 8,000 patients evaluated at 7 medical centers, developed by a co-investigator ([name]) along with the PI.^{47,56-59}

[figure not shown]

Figure 2. Cumulative hazard plot for 1-year mortality for patients with and without Contrast-Induced Nephropathy (CIN), adjusted for age and the presence of an active malignancy at the time of enrolment. ($p < 0.01$).

evaluated simultaneously for both suspicion of acute coronary syndromes and PE. In patients at low and moderate risk of PE (pre-test VTE risk $\leq 20\%$), the rate of AKI consistent with CIN, did not differ with the presence (9%) or absence (8%) of a VTE.

The PI has developed methods of risk-stratifying patients for CIN in the emergency care setting: Using data from her contrast-enhanced CT cohort of patients treated in the emergency care setting, the PI evaluated over 100 literature derived risk factors (at varying thresholds) for CIN^{18,23,28,41,60-83} and derived the AKIrisk Score: 2 points for glycosuria on urine dipstick; and 1 point each for Age ≥ 50 years, measured diastolic blood pressure ≥ 100 mmHg, history of HIV or AIDS, and a history of coronary artery disease.⁸ Importantly, an elevated creatinine (SCr), corresponding to an estimated glomerular filtrate rate (eGFR_{SCr}) ≤ 60 ml/min/m²,¹⁷ did not accurately risk-stratify patients for CIN: sensitivity 13%, area under the receiver operating characteristic curve (AUROC) 0.55.^{9,10} In comparison, a AKIrisk Score of ≥ 2 points more accurately predicted CIN: sensitivity 56% (95% CI 43 to 68%), specificity 81% (95% CI 77 to 84%), AUROC of 0.74 (95% CI 0.68 to 0.81) and positive predictive value (27%, 95% CI 20 to 34%).⁸⁻¹⁰ (Figure 4)

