Figure 4. Outcomes (prospective) for patients (n=633) undergoing contrast-enhanced CT imaging, risk-stratified by the AKIrisk Score. Major Adverse Events were as defined as death, renal failure, acute myocardial infarction, cerebral vascular accident and/or other arterial vascular event requiring surgical or medical intervention.

group randomized to VQ will be lower in the proposed study. Importantly, despite a lower physician-estimated (unstructured) risk, the rate of AKI was significantly higher in the CTPA group.

Table 3. Preliminary data demonstrating an increased risk of acute kidney injury (AKI) with contrast media exposure.

	CTPA Imaging N=100*	VQ Imaging N=100*
	Exposed to Contrast Media	Unexposed Control
AKIrisk Score ≥ 2 points, % (95% CI)	72 (62 to 81)	86 (77 to 92)
Acute Pulmonary Embolism on Imaging Study, % (95% CI)	8 (4 to 15)	10 (5 to 18) [†]
Acute Kidney Injury, % (95% CI)	32 (23 to 42)	6 (2 to 13)

*Median Age 73 years (IQR 20), Black Race 42%, Median eGFR 37 ml/min/m² (IQR 28)

† VQ imaging studies interpreted as intermediate risk for acute pulmonary embolism in an additional 3 patients.

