1.6 Known Potential Risks

400 patients enrolled in this study will go on to complete the CTPA (300 with a AKIrisk Score ≥ 2 after random assignment and 100 with a AKIrisk Score < 2) and, as ordered, and will have an exposure to contrast media as a result of usual care. The remaining 300 patients will undergo VQ imaging, which has equivalent diagnostic accuracy for PE (in patients with a pre-imaging risk of PE $\leq 20\%$ and a normal chest radiograph) and the same or lower risks of exposure to ionizing radiation as CTPA.^{50,53,54} Patients may provide a urine sample and could have as many as two blood draws, which is associated with minimal risk. Importantly, these patients will already have intravenous access placed in preparation for the diagnostic imaging, as part of their usual medical care. Thus, for the majority of patients, the first blood sample may not require an additional needle stick.

The decision of whether or not to enroll could induce psychic stress to the patient at a time when they are already afraid. The PI and co-investigator ([name]) have conducted telephone follow-up with patients treated in the emergency care setting as proposed here on over 4,000 patients with no patient complaints or evidence of distress.^{11,20,47,103} From prior experience, we estimate that 60% of patients will have primary family members present at the time of informed consent. Patients will be informed on the potential increase in time spent in the emergency department during the informed consent process. There may also be a potential loss of confidentiality. Clinical data will be collected by trained study personnel who are listed on the IRB approved protocol and all data will be kept in a secure electronic format. The PI, research coordinator and data analyst. Research assistants will have limited access and only as needed to assist with screening, enrollment, and coordination of follow-up. We will redact PHI from records that might be examined by non-study personnel.

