We will reject the null hypothesis and the two groups, CTPA and VQ, will be considered equivalent if

$$\frac{\hat{P}_1 - \hat{P}_2 - \delta}{\sqrt{\hat{P}_1(1 - \hat{P}_1)/n_1 + \hat{P}_2(1 - \hat{P}_2)/n_2}} < -z_{0.05} \quad \text{and} \quad \frac{\hat{P}_1 - \hat{P}_2 + \delta}{\sqrt{\hat{P}_1(1 - \hat{P}_1)/n_1 + \hat{P}_2(1 - \hat{P}_2)/n_2}} > z_{0.05}$$

If we reject the hypothesis of equivalency, we will conduct an analysis for a superior trial. Hence, for comparison with the dichotomous primary outcome, that is, whether a subject develops AKI at the 2-7 day follow-up, a logistic regression model will be used. Group comparisons will be adjusted for baseline covariates. To validate the decision rule in classifying subjects into a low-risk group we will: 1) Measure the AKI rate in the low-risk group (AKIRisk Score <2) with a desired margin of error. We assumed the upper limit of the one-way 95% confidence interval to be <10%, based on preliminary data, and prior literature.^{6,7} as such, we will compute the one-way 95% confidence interval using a Z test statistic; and 2) Compute sensitivity and specificity of the decision rule.

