3.1 Number of Study Subjects

We will identify and enroll 2 groups of patients:

- 1) 100 patients undergoing CTPA with an estimated risk of CIN $<10\%$ (AKIrisk Score <2).
- 2) 600 patients with an AKIrisk Score ≥ 2 , randomized to CTPA (exposure to iodinated contrast media) or VQ imaging (unexposed control).

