Patients will be enrolled in the emergency departments of five hospitals: 1. IUH Methodist Hospital (which also provides emergency care services at IUH University Hospital), 2. Eskenazi Health (formerly Wishard) Hospital, IUH Ball Memorial Hospital, University of Utah, and Intermountain Healthcare. Patients may also complete their imaging studies and, for patients hospitalized >48 hours, may complete their initial follow-up at IUH University Hospital. Examination of data for all emergency department patients who have had a CTPA scan ordered from the two enrollment sites over the past three years reveals mean age 49 ± 16 years with 54% African American, 44% Caucasian, 0.8% Asian, 1% American Indian 1% report Hispanic Ethnicity, and 51% are females; payers include Medicare (22%), Medicaid (25%), Private or commercial insurance (19%) and self-pay (34%). The patients have a high burden of comorbidities, and approximately 65% of all patients are admitted to the hospital. These demographic data match up well with those published in the last three National Hospital Ambulatory Medical Care Surveys (NHAMCS)—a survey designed to collect data on the utilization and provision of ambulatory care services in hospital emergency and outpatient departments. Findings are based on a national sample of visits to the emergency departments and outpatient departments of non-institutional general and short-stay hospitals.⁹⁸⁻¹⁰⁰ Additionally, the table below shows the demographic characteristics of a large sample of patients evaluated for possible PE in 12 emergency departments, not including any hospitals in Indianapolis.¹⁰¹ The almost 2:1 predominance of women undergoing CTPA scanning from the emergency department setting has been shown repeatedly in the United States, and to a lesser extent, in Europe.^{55,102}

Demographics of Patients Evaluated for Pulmonary Embolism in the Emergency Care Setting

12 Centers Not Including Indianapolis

Indianapolis

	n = 7940		n = 200
	n	% or Mean	% or Mean
Age		49±16	49±16
Female	5328	67%	65%
White	4541	57%	61%
Black	2704	34%	29%
Hispanic	482	6%	9%
Asian	74	1%	1%
Other Race	139	2%	<1%

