4.2 Inclusion Criteria

1. Age ≥ 18 years
2. CTPA ordered by the treating provider to evaluate PE.
3. Pre-test probability of PE $\leq 20\%$ (defined using the PE Pretest Consult Score)
4. For randomization to CTPA or VQ imaging: Pre-imaging CIN risk $\geq 20\%$ (AKIrisk Score ≥ 2 points)

- A lower-risk subset of 100 patients (AKIrisk Score <2) will be enrolled and followed. These patients will complete the CTPA as ordered by their provider (not randomized). Data from this lower-risk subset, along with high-risk patients randomized to CTPA will be used will be used to validate the AKIrisk Score, alone and in combination with NGAL and eGFR_{CYS} (Study Aims 1 and 3).

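### Sensitivity and specificity of the AKIrisk Score are planned without weighting in a sample whose score mix is fixed by quota

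*Combined protocol and SAP*

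**What the plan says.** The primary outcome analysis in section 2.1 validates the decision rule in two steps. Item 1 estimates the AKI rate among patients scoring below 2, with a one-sided upper 95% limit. Item 2 is the single instruction to "Compute sensitivity and specificity of the decision rule".

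Enrolment is fixed by that score. Section 1.6 gives the composition of the CTPA patients as "300 with a AKIrisk Score ≥ 2 after random assignment and 100 with a AKIrisk Score < 2", and sections 3.1 and 4.2 set the same quotas.

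The validation set is described in two ways. Section 4.2 states: "Data from this lower-risk subset, along with high-risk patients randomized to CTPA will be used", which makes 400 patients. The Précis describes validation "in both the exposure and unexposed controls, as well as, an additional non-randomized 100 subjects who will undergo CTPA for suspected PE", which makes 700.

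No section weights the strata back to the eligible CTPA population, and none plans to record how the score is distributed in that population.

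**The concern.** Sensitivity is the share of AKI cases that had a high score, and specificity is the share of non-cases that had a low score. Both mix the two score groups, so both depend on how many patients of each kind are in the sample. Here that number is a design choice. Predictive values are computed within a score group and survive this sampling; sensitivity and specificity do not.

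Validating the score is secondary objective 1 and a stated study outcome in section 1.2. Readers will naturally set the trial's figures beside the derivation values in section 1.5 (56% and 81%). An apparent gain in sensitivity and loss of specificity could then come entirely from the enrolment ratio.

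**Working it through.** **The plan's own figure.** The only numerical target for validation is the upper limit of 9.3% in section 2.2, for a 5% low-score AKI rate. With 100 patients less 30% dropout, n = 70: 0.05 + 1.645 × √(0.05 × 0.95/70) = 9.28%. This reproduces it. It concerns a risk within one score group, so the quota does not affect it.

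**Inputs.** Section 1.5 gives sensitivity 56%, specificity 81% and positive predictive value 27% at a score of 2 or more, and CIN incidence over 10% in the contrast-CT cohort. I assume 11%, which agrees with the 27%:

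- share scoring 2 or more = 0.56 × 0.11 + 0.19 × 0.89 = 0.231
- AKI risk at 2 or more = 0.0616/0.2307 = 26.7%, taken as 27%
- AKI risk below 2 = 0.0484/0.7693 = 6.3%

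**Crude result in the trial's 300 + 100.** Expected cases are 300 × 0.27 = 81 and 100 × 0.063 = 6.3. Expected non-cases are 219 and 93.7.

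- sensitivity = 81/(81 + 6.3) = 92.8%
- specificity = 93.7/(93.7 + 219) = 30.0%

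Incidence of 10% to 15% gives 92.9%/29.4% to 92.2%/31.6%. The 5% low-score rate from section 2.2 gives 94.2%/30.3%. Equal 30% dropout in both strata changes nothing.

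**What the ratio alone produces.** Equal risks in both groups give exactly 75%/25%. For any score whose high group has at least the risk of its low group, crude sensitivity cannot be under 75%, nor specificity under 25%. Risks of 20% and 10% give 60/70 = 85.7% and 90/330 = 27.3%.

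**Correctly weighted values.** With true high-score share s, sensitivity = 0.27s/(0.27s + 0.063(1 − s)) and specificity = 0.937(1 − s)/(0.937(1 − s) + 0.73s).

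| True share with score ≥2 | Weighted sensitivity / specificity |
|---|---|
| 23% | 56% / 81% |
| 30% | 65% / 75% |
| 40% | 74% / 66% |
| 50% | 81% / 56% |
| 60% | 87% / 46% |
| 72% | 92% / 33% |

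The crude 92.8%/30.0% is compared with whichever row is true.

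**Which share is plausible.** The 23% is implied by an unselected contrast-CT cohort. Table 3 shows 72% (95% CI 62 to 81), but in CTPA patients matched to VQ patients, with median age 73. For CTPA scans "ordered from the two enrollment sites over the past three years reveals mean age 49 ± 16 years" (section 4.1). If ages are normally distributed, 47.5% are 50 or older. Suppose every one of them had a further point. A 72% share would still need (0.72 − 0.475)/0.525 = 47% of those under 50 to reach 2 points without the age point. The lower limit of 62% would need 28%.

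**If VQ patients are pooled (600 + 100).** With 6% AKI after VQ (Table 3), high-score cases are 81 + 18 = 99. Sensitivity is 99/105.3 = 94.0% and specificity 93.7/(93.7 + 501) = 15.8%. With 27% after VQ, the figures are 162/168.3 = 96.3% and 93.7/(93.7 + 438) = 17.6%.

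**The case against.** The plan never says unweighted; that is read from its silence. This is fair, but weighting needs the score mix among eligible patients, which no section plans to record. Followed as written, the plan yields the crude figures.

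The 93%/30% contrast is one scenario. Section 1.5 also reports 15% CIN in patients undergoing CTPA. If risks of 27% and 6.3% hold, that implies a share of (15 − 6.3)/(27 − 6.3) = 42% and weighted accuracy of about 76%/64%, so the gaps are about 17 and 34 points. If 56%/81% holds at 15% incidence instead, the share is about 25% and the large gap returns. The age argument also rests on all CTPA orders at two sites, not on trial-eligible patients. So the mechanism is certain and its size is not.

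Aim 1 and the sizing of the low-score group rest on the low-score AKI rate, which is sound, and no decision in the plan depends on sensitivity or specificity. That limits the seriousness. It does not make the reported figures right.

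Weighted estimates would still describe a restricted population (pre-test PE risk of 20% or less, chest-radiograph exclusions), so they would not be fully comparable with the derivation cohort. This also stands.

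**Conclusion.** The concern holds and should be fixed. Computed as the plan reads, sensitivity and specificity would largely reflect the 3:1 quota. Against crude values near 93%/30%, the error is about 37 points of sensitivity and 51 of specificity at a true high-score share of 23%. It is 12 and 26 points at 50%, and small near 72%. These sizes assume AKI risks of 27% and 6.3% by score group, taken from section 1.5 with 11% incidence. The true share is unknown; the site age data make a value near 72% unlikely but do not settle it. AKI risk within each score group, the low-score upper limit and the randomized comparison are not affected. The Précis and section 4.2 also conflict on the validation set, and pooling VQ patients would lower crude specificity further, to about 16% to 18%.

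**What to change.** - In item 2 of the validation analysis (section 2.1), weight each score stratum by the inverse of its sampling fraction.
- Take the fraction from a screening-log tally of otherwise eligible CTPA patients by score (below 2, 2 or more, or not scorable for want of a urine result), over the period when both strata are open.
- Use bootstrap intervals that include the uncertainty in the tally. If the fraction stays uncertain, show weighted results over a stated range of shares, for example 23% to 72%.
- Apply the same weights to any AUROC that is reported.
- Lead with AKI risk in each score group among patients assigned to CTPA.
- Reconcile the Précis with section 4.2 on who forms the validation set.

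The cost is SAP wording and the tally. Under section 4.1 coordinators already complete the score, and a dipstick where needed, to determine eligibility, so no extra tests are required. At a 23% share with no refusals, the 100 low-score places fill after about 100/0.77 = 130 eligible patients, which fixes the share to about 16% to 30%.

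The real price is precision, because only about 6 low-score AKI cases are expected. At a 23% share, simulated 95% intervals for sensitivity with 300/100 patients widen from about 87–98% (crude) to 40–81% (weighted). Including the tally, they are about 37–81%, with specificity 74–87%. After 30% dropout (210/70), weighted sensitivity spans about 38–86% before tally uncertainty. The narrow crude interval would hide how little 100 low-score patients can say about sensitivity.

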2.2 Secondary objectives

The secondary objectives of this study are to:

- 1) Validate the AKIRisk score, alone and in combination with acute-phase markers of renal dysfunction (Cystatin-C and/or NGAL), to inform imaging strategies and reduce the risk of AKI.
- 2) Compare the incidence of short, mid- and long-term AKI and subsequent health outcomes in patients exposed to iodinated contrast media and unexposed controls at 30-days and at 1-year.
- 3) Measure the 30-day and 1-year incidence of VTE and subsequent severe health outcomes including outcomes related to VTE and VTE treatment.

All secondary outcomes will be defined using composite outcomes and will be determined to be present or absent by the agreement of 2 of 3 blinded physician reviewers, using methods of adjudication successfully employed by the PI in comparable studies.^{7,11,20,46,53,59} Briefly, physician reviewers will be provided with copies of the EMR and patient interview responses. Identifying information will be redacted, and, while the reviewer will have access to any creatinine values recorded in the EMR, they will not be provided with creatinine measurements performed for the study and not recorded in the EMR, nor will they be informed of the subject's status with regard to the primary outcome. Each reviewer will be asked to define each secondary outcome as present or absent, without knowledge of the other reviewers' determinations. In the event of a disagreement between the first and second reviewer, the determination of a third reviewer will be used to define the outcome. No reviewer will be made aware of their designation as the first, second or third reviewer.

Acute Kidney injury will be reported using defined using the Acute Kidney Injury Network (AKIN) definitions (stages 1-3).⁹⁰ KDIGO guidelines do recommends a more standard definition of AKI than for CIN.³⁸ While we do agree with this recommendation, in principle, we are planning a study aimed at changing imaging practices of physicians in specialties that are not as familiar with the. We do plan to measure and report AKIN 1-3 outcomes. We also plan the enrollment of a heterogeneous cohort of patients with renal function ranging from normal to significantly impaired and patients with a range of acute and chronic illnesses of varying severity, consistent with patients treated in the emergency care setting.

Venous Thromboembolism (VTE) including PE and/or DVT will be defined by the identification of one or more thrombus, requiring medical or surgical intervention, in the deep veins of the extremities or in the pulmonary vasculature as determined by ultrasonography, echocardiography, CT, MRI, VQ or on autopsy. We will also record and report severe outcomes secondary to VTE and treatment of VTE, including hemorrhage from anticoagulant treatment.

Complications of PE imaging will be defined for the first 24 hours after imaging, patients will be followed for one or more of the following recorded in the EMR, and requiring medical or surgical intervention: hypotension defined as a SBP ≤90 mmHg or ≥10% below baseline, dyspnea, acute pulmonary edema or hypervolemia, oral swelling, rash or puritis, abdominal pain, nausea or vomiting, altered mental status, or soft tissue contrast media or radio-isotope extravasation. The PI has previously published these methods of outcome determination.⁵³

Severe Health Outcomes will be defined for each follow-up period (24 hours, 2-7 days, 30 days, and 1 year) as the combined outcome of death from any cause, renal failure, acute myocardial infarction, stroke, and/or one or more symptomatic complications of arterial-vascular disease, in any distribution, (cerebral, coronary, mesenteric, renal or peripheral) requiring surgical or medical therapy.²⁸ Renal failure will be defined by the AKIN 3 criteria: an increase in creatinine 3 times baseline, or a decrease in eGFR_{Scr} $\geq 75\%$, or an absolute increase in creatinine to ≥ 4.0 mg/dL as a result of an increase of at least 0.5 mg/dL, or the need for renal replacement therapy.⁹⁰ The highest recorded creatinine recorded in the EMR during the follow-up period will be used to determine this outcome. Myocardial infarction will be defined as a cardiac catheterization, autopsy or cardiac imaging study demonstrating acute coronary thrombus or non-viable myocardium; or at least one measured troponin I above the 99th percentile and clinical findings consistent with ischemia; or diagnostic ECG findings including acute ST-T changes, new left bundle branch block, or new pathologic Q-waves.^{96,97} Stroke will be defined as an acute, focal neurologic deficit with symptoms lasting longer than 24 hours and/or imaging or autopsy evidence of acute cerebral infarction. Finally, coronary or cerebrovascular events not meeting the criteria for acute myocardial infarction or stroke, including acute coronary syndromes and transient ischemic attack (TIA), are included within the definition of other arterial vascular events if these events required medical or surgical invention. The PI has successfully applied the same methods of outcome determination in a comparable study.^{7,11,20}

Outcomes involving death will be classified by adjudicators as: 1) Renal injury as a significant contributor defined as obvious evidence of renal failure defined by worsening azotemia with complications of renal failure including oliguria, pulmonary edema, hyperkalemia, pericardial effusion, or the need to initiate renal replacement therapy before death; 2) Death from VTE and/or hemorrhage requiring intervention following anticoagulant treatment for VTE; or 3) Unrelated to VTE or Renal injury. Death outcomes 1) and 2) may be identified concurrently.

Sample Size We will use a prospective validation study design for the previously derived decision rule (AKIrisk Score), classifying subjects into low AKI-risk group. We will recruit 100 subjects undergoing CTPA with an AKIrisk Score <2 . Since the overall AKI rate in our patient population of interest is $<10\%$ (see *Preliminary Data*), the group of subjects with AKIrisk Score <2 will have much lower AKI rate. Assuming 5% AKI rate in this low risk group, the upper limit of one way 95% confidence interval will be $\leq 9.3\%$ with a sample size of 100 (adjusted for dropout and screening failures).

Secondary Outcome Analysis: We will measure several secondary outcomes of which almost all are dichotomous (e.g. death, renal failure, stroke and/or other acute arterial vascular events). We will use a logistic regression model including the baseline covariates in the model. In case of rare events, we will use an exact logistic regression analysis. For the change in continuous outcomes, we will use ANCOVA model including the baseline covariates. Using similar analyses, we will compare baseline outcomes between enrolled subjects and subjects who will meet the inclusion criteria but decline participation in the study. Finally, we will compare outcomes of patients, relative to the AKIrisk Score, and we will compare outcomes and demographic data of those who enroll versus those who meet inclusion but decline participation to assess for possible bias induced by the informed consent process.⁸⁴

